3.1.2 Vorapaxar Treatment

Subjects that have received a confirmation of laboratory results and inclusion criteria in the antiplatelet naïve (group 1) group and those who have completed the run-in period with adherence to treatment (no more than 2 doses missed) with EC ASA and/or clopidogrel and who wish to continue in the study will receive vorapaxar 2.08mg daily for 30 ± 7 days. Subjects will be instructed with regards to any interactions the study drugs may have with other medications the subject is taking or may have at home. This will be in addition to the standard treatment assigned to each group as shown below:

- Group 1: vorapaxar 2.08mg orally once daily
- Group 2: clopidogrel 75mg orally once daily + vorapaxar 2.08mg orally once daily
- Group 3: EC aspirin 81mg orally once daily + vorapaxar 2.08mg orally once daily
- Group 4: EC aspirin 81mg orally once daily + clopidogrel 75mg orally once daily + vorapaxar 2.08mg orally once daily

3.1.3 Identity of Study Treatment

All study drugs will be labeled in the local language according to the requirements of local law and legislation. A complete record of batch numbers and expiry dates of all study treatment as well as the labels will be maintained in the site's study file.

3.2 Dosage and Administration

Vorapaxar 2.08mg will be taken orally once daily with or without food.

Subjects in group 2 will receive 75 mg orally daily with or without food.

Enteric coated (EC) aspirin 81 mg will be taken orally once daily. EC aspirin should not be crushed or chewed and is to be taken with a full glass (8oz) of water with or without food.

All study treatment will be generally taken in the morning. Subjects who missed a study treatment dose need to take the missed dose as soon as they remember. Skip the missed dose if it is almost time for the next scheduled dose. Do not take an extra dose to make up for the missed dose.

Assigned study drug treatments for each group are specified in section 3.1.1 and 3.1.2.

3.3 Dose Modifications

The investigator should permanently stop the study drug for a given subject if continuation is deemed to be detrimental to the subject's well-being. Permanent study drug interruption should be recorded on the corresponding case report form giving the date and primary reason for the permanent discontinuation of study drug.

3.4 Drug Logistics and Accountability

All study drugs will be stored at the investigational site in accordance with GCP and Good Manufacturing Practices (GMP) requirements. Tablets will be stored as according to the manufacturer's instructions and will be inaccessible to unauthorized personnel. Special storage conditions and a complete record of batch numbers and expiry dates can be found in the sponsor's study file. The responsible site personnel will confirm the condition, date and time of receipt of study drug and will use the study drug only within the framework of the clinical study protocol. Receipt, distribution, return, and destruction of study drugs will be documented and filed as according to the site's standard operating procedures.

3.5 Treatment Compliance

The investigator should promote compliance by counseling the subjects to take the study drug as prescribed. The subjects will be instructed to contact the appropriate site personnel if unable to comply with study drug instructions. Treatment compliance will be assessed by reviewing a study drug diary during the run-in period and by mandatory study drug pill count on visits 2, 3, and 4. Study drug compliance should be documented on the appropriate case report form.

3.6 Prior and Concomitant Therapy

Vorapaxar increases the risk of bleeding in proportion to the subject's underlying bleeding risk and use of certain concomitant medications (chronic nonsteroidal anti-inflammatory drugs [NSAIDs], selective serotonin reuptake inhibitors, serotonin norepinephrine reuptake inhibitors) can increase the risk for bleeding. Careful consideration of each potential subject's overall health status, medical history, and concomitant medications will be given by the investigator after a thorough review to ensure subject's appropriateness for enrollment.

Vorapaxar is eliminated primarily by metabolism with contributions from CYP3A and CYP2J2. Strong CYP3A inhibitors increase and inducers decrease vorapaxar exposure.

Subjects who are taking CYP3A inhibitors, CYP3A inducers, warfarin and other anticoagulants, antiplatelet medications except for clopidogrel, oral factor Xa inhibitor, or oral direct thrombin inhibitor and subjects who are planning to start treatment on these medications are not eligible for enrollment.

4 STUDY METHODS

4.1 Reactive Hyperemia-Peripheral Arterial Tonometry (RH-PAT)

Noninvasive flow-mediated vasodilation (FMD) is a widely used method to assess endothelial function, but its technical difficulty and problems remain obstacles for use in clinical practice. Reactive hyperemia-peripheral arterial tonometry (RH-PAT) was developed as a simpler and more reproducible method. Endothelial function will be assessed using the ENDOPAT system (Itamar Medical Ltd) at pre-dose (Visit 2) and after 3-4 weeks of maintenance therapy (Visit 4).

4.2 Blood and Urine Sampling

Phlebotomy sites will be carefully chosen to minimize risk and the blood will be collected into Vacutainer® tubes (Becton-Dickinson, Franklin Lakes, NJ). After discarding the first 2-3mL of free flowing blood, the tubes will be filled to capacity and gently inverted 3 to 5 times to ensure complete mixing of the anticoagulant. Tubes containing 3.2% trisodium citrate (n=2) will be used for light transmission aggregation, Calibrated Automated Thrombogram and for platelet/ endothelial and inflammatory biomarker assays. One 17 USP/mL lithium heparin tube will be used for TEG-6S Platelet Mapping assay.

4.3 CORA TEG-6S

The CORA instrument is a microfluidic cartridge-based device capable of performing all current thromboelastographic assays. It is a fully automated cartridge-based system, replacing the cups and pins of the TEG5000 and eliminating potential user error in pipetting and reagent constitution. Unmetered samples are transferred into the cartridge using a disposable dropper or transfer pipette. There are up to four simultaneous channels per cartridge, and the system requires less than 70µl of blood for one channel, and less than 280µl for four channels, versus 360µl for one TEG channel. To perform a test, a disposable CORA Cartridge is inserted into the instrument. Blood or WQC material is added to an entry port on the cartridge and drawn into the cartridge under instrument control. Once in the disposable, the sample is automatically metered into as many as four separate analysis channels, depending upon the assay being performed. Reconstitution of reagents dried within the cartridge is accomplished by moving the sample through reagent wells, under the control of microfluidic valves and bellows within the cartridge. After each sample has been mixed with reagent, Cora Hemostasis Analyzer System (Cora®) will be used to assess qualitative and quantitative assessment of the hemostasis. Two cartridges will be used in the study.

Citrated Multi-Channel cartridge is used to measure hemostasis including thrombin generation kinetics (Table). The assay cartridge uses a citrated blood sample that is mixed with dried reagents within each of the 4 channels, each with calcium chloride (to reverse the sodium citrate) and : 1)

kaolin, 2) kaolin + tissue factor activated (RapidTEG), 3) kaolin + heparinase, and 4) kaolin + abciximab (functional fibrinogen).

R	Period of time of latency from the time that the blood was placed in the TEG® analyzer until the initial fibrin formation. This represents the enzymatic portion of coagulation.
K	K time is a measure of the speed to reach a certain level of clot strength. This represents clot kinetics.
α	Measures the rapidity of fibrin build-up and cross-linking (clot strengthening). This represents fibrinogen level.
MA	Maximum Amplitude is a direct function of the maximum dynamic properties of fibrin and platelet bonding via GPIIb/IIIa and represents the ultimate strength of the fibrin clot. This represents platelet function/aggregation.
TMRTG	Time to maximum rate of thrombus generation.
MRTG	Maximum rate of thrombus generation.
TG	Total thrombus generated.
TMRL	Time to maximum rate of lysis.
MRL	Maximum rate of lysis.
L	Total lysis.
D	Delta is the difference between R time and the time of initial split point (SP, mins) of the TEG tracing (R – SP), representing the time interval of greatest clot growth secondary to peak thrombin generation.

The PlateletMapping (PM) cartridge is used to monitor response to oral antiplatelet agent including ASA and plavix. The cartridge employs a heparinized blood sample that is mixed with dried reagents within each of the 4 channels of the cartridge: 1) kaolin + heparinase, 2) Activator F + abciximab, 3) ADP + Activator F, and 4) AA + Activator F.

4.4 Calibrated Automated Thrombogram® (CAT) System:

Calibrated Automated Thrombogram® (CAT) System: Lag time, peak thrombin production, mean velocity rate index, and endogenous thrombin potential (ETP) will be assessed by calibrated automated thrombogram in platelet poor plasma (Thrombinoscope by Stago).

4.5 Platelet aggregation (Chronolog)

The blood-citrate tubes will be centrifuged at 120g for approximately 5 minutes to recover platelet-rich plasma and will be further centrifuged at 850g for approximately 10 minutes to recover platelet-poor plasma. The platelet rich plasma and platelet-poor plasma will be stored at room temperature to be used within 2 hours of blood collection.

Platelet aggregation will be assessed using Chronolog Lumi-Aggregometer (model 490-4D) with the AggroLink software package. Platelets in platelet rich plasma will be stimulated with 5µM ADP-, 15µM SFLLRN(PAR-1) -and 4µg/ml collagen- induced maximal and final aggregation values (aggregation at 6 minutes) will be recorded with platelet-poor plasma used as a reference.

4.6 Plasma Platelet/Endothelial and Inflammatory Biomarkers

After collection plasma and serum samples will be batched and frozen at -70C at each time point. Plasma platelet/endothelial and inflammatory biomarkers measurements to be performed in the study include high sensitivity C-reactive protein (hsCRP), fibrinogen, von Willebrand factor (vWF), interleukin (IL)-6, p-selectin, plasminogen activator inhibitor (PAI)-1, matrix metalloproteinase (MMP)-9).

Serum samples will be batched and shipped on dry ice for analysis by Corgenix Medical Corp. (Broomfield, CO) for measurements of oxidized LDL- α 2 glycoprotein I complex, a pro-atherothrombotic antigen.

4.7 CYP2C19 Buccal Swab Genotyping

CYP2C19 Buccal Swab Genotyping Study subjects considered for clopidogrel groups (Group 2 and 4) will have a CYP2C19 buccal swab analysis performed at screening. Poor cytochrome P450 2C19 metabolizers (*2/*2) will be a screen failure and discontinue the study.

The Spartan RX CYP2C19 System is indicated for use as an aid to clinicians in determining therapeutic strategies for therapeutics that are metabolized by the Cytochrome P450 2C19 gene product, and that are specifically affected by the *2, *3, and *17 alleles. The Spartan RX CYP2C19 Assay will be run on the Spartan RX CYP2C19 Platform from the buccal sample collected with a buccal swab.

4.8 Study Treatment/Intervention-

This phase IV, open label, pharmacodynamic investigation will be conducted in patients between 18-75 years of age with multiple coronary artery disease risk factors (antiplatelet naïve patients) and patients with prior MI or PAD on antiplatelet therapy (Figure 1). Informed consent will be obtained from subjects meeting the inclusion criteria before the initiation of any study-specific procedures. Subjects will be grouped according to their current antiplatelet regimen. Subjects with cardiovascular risk factors not on antiplatelet therapy will be included in either Group 1 or 2. Patients on ASA alone will be included in Group 3 and patients on dual antiplatelet therapy will be in Group 4.

- Group 1 (control group): vorapaxar 2.08mg orally once daily
- Group 2: clopidogrel 75mg orally once daily + vorapaxar 2.08mg orally once daily
- Group 3: EC aspirin 81mg orally once daily + vorapaxar 2.08mg orally once daily
- Group 4: EC aspirin 81mg orally once daily + clopidogrel 75mg orally once daily + vorapaxar 2.08mg orally once daily

The study comprises 6 periods: screening, run-in (for subjects in groups 2, 3, and 4), onset and maintenance, offset, and end of study (Figure 1). The trial will require clinic visits at screening, vorapaxar dosing day, 24 hours post initial vorapaxar dosing, 3-4 weeks post-dosing, 2 weeks post vorapaxar discontinuation, and 4 weeks post vorapaxar discontinuation. Patient instructions for the run-in phase will be given during the screening visit. One day prior to the run-in, the study coordinator will call the subject to remind subjects of run-in instructions.

Pharmacodynamics will be assessed at multiple time points to assess onset-, maintenance-, and offset-effect of vorapaxar on thrombin generation, platelet reactivity, and plasma/platelet endothelial and inflammatory biomarkers. Safety assessment will be assessed throughout the study. Approximately 25-30ml of blood will be drawn at each visit. Phlebotomy sites will be carefully chosen to minimize risk. See schedule of procedures in section 7 for detailed schedule of study events.

4.9 Consent

Eligible subjects may only be included in the study after providing written (witnessed, where required by law or regulation), IRB/IEC/REB-approved informed consent, If the subject is capable of doing so, he/she should indicate assent by personally signing and dating the written informed consent document or a separate assent form. Informed consent must be obtained before conducting any study-specific procedures (i.e., all of the procedures described in the protocol). The process of obtaining informed consent should be documented in the subject source documents.

5 STATISTICAL CONSIDERATIONS/DATA ANALYSIS

5.1 Sample Size

This is an exploratory study; we assume that a sample size of 25 qualified subjects (see study schematic) in each group is sufficient to assess the difference in platelet inhibitory effect of vorapaxar 2.08 mg, administered alone or in addition to an antiplatelet agent (clopidogrel 75mg), and/or acetylsalicylic acid 81mg.

5.2 Primary and Secondary Analysis

5.2.1 Primary Analysis

The primary endpoint measures are a change in platelet-fibrin clot generation kinetics by thrombelastography (R, TIP-FCS, TG) and thrombin generation kinetics (Lag time, peak thrombin production, time to peak thrombin generation, and endogenous thrombin potential) as measured by calibrated automated thrombogram at maintenance therapy (3-4 weeks vorapaxar treatment) compared to pre-dose within and between each treatment group.

5.2.2 Secondary Analysis

Secondary Analysis endpoint measures are a change in:

- Platelet-fibrin clot generation kinetics by thrombelastography (R, TIP-FCS, TG) at onset and offset vorapaxar treatment compared to pre-dose within and between each treatment group.
- Thrombin generation kinetics (Lag time, peak thrombin production, time to peak thrombin generation, and endogenous thrombin potential) as measured by calibrated automated thrombogram during onset and offset of vorapaxar treatment compared to pre-dose within and between each treatment group.
- 5 μ M ADP-, 15 μ M SFLLRN (TRAP)-and 4 μ g/ml collagen- induced maximal and final aggregation by light transmittance aggregation during onset, maintenance, and offset of vorapaxar treatment compared to pre-dose within and between each treatment group. ADP-and

AA-induced aggregation by TEG-6S Platelet Mapping assay during onset, maintenance, and offset of vorapaxar treatment compared to pre-dose within and between each treatment group.

- Platelet/endothelial and inflammatory biomarkers during onset, maintenance, and offset of vorapaxar treatment compared to pre-dose within and between each treatment group. Reactive hyperemia index (RHI) as assessed using the ENDOPAT system between pre-dose and maintenance therapy within and between the treatment groups.

6 Statistical calculations

Statistical calculations will be carried out using SAS® for Windows, version 9.3 or later (Cary, NC). Within group analyses of change scores (pre and post vorapaxar) will be performed using a paired t-test, or the Wilcoxon signed ranks test if the change scores are sufficiently non-normal. The Shapiro-Wilk test will be used to determine if the change scores are non-normal. A calculated P-value < 0.05 will be considered a significant difference between treatments. A secondary ANCOVA analysis will be performed in each group to examine the factors that explain potential variations in change scores, and model variables will include the baseline test value, age, sex, race, weight, diabetes, antiplatelet response to EC ASA and clopidogrel, smoking, etc.

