2.2 Number of Subjects

Multiple cohorts of subjects may be utilized in order to achieve the target enrollment number of 100 subjects (25 qualified subjects in each study group) with valuable data.

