8.5 Subject Withdrawal

Subjects should also be withdrawn at any time if the investigator concludes that it would be in the subject's best interest for any reason.

Subjects may be considered withdrawn if they fail to return for visits, or become lost to follow up for any other reason. For subjects who are lost to follow-up (i.e., those subjects whose status is unclear because they fail to appear for study visits without stating an intention to withdraw), the investigator should show "due diligence" by documenting in the source documents steps taken to contact the subject (e.g. dates of telephone calls, registered letters). Subjects who are prematurely withdrawn from the study will not be replaced.

8.5.1 Subject Withdrawal Documentation.

If premature withdrawal occurs for any reason, the investigator should attempt to determine the primary reason for the withdrawal. The date and primary reason for premature withdrawal will be recorded on the Study Summary CRF. If applicable, the Investigator must provide appropriate follow-up medical care for all subjects who are prematurely withdrawn from the study, or must refer them for appropriate ongoing care.

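### Section 6 lets a Shapiro-Wilk test choose between the t-test and Wilcoxon, with no rule to keep one test per measure, so the four groups can be tested differently on the same measure

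*Combined protocol and SAP*

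**What the plan says.** Section 6 (Statistical calculations) states: "Within group analyses of change scores (pre and post vorapaxar) will be performed using a paired t-test, or the Wilcoxon signed ranks test", the latter "if the change scores are sufficiently non-normal". It continues: "The Shapiro-Wilk test will be used to determine if the change scores are non-normal". No significance level is attached to the Shapiro-Wilk test, and the degree of non-normality that triggers the switch is not defined. No transformation is named, and neither is a sensitivity analysis with the other test.

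Section 5.2.1 lists seven primary measures: three from thrombelastography and four from the calibrated automated thrombogram. Their changes at maintenance are to be "compared to pre-dose within and between each treatment group". Section 5.2.2 extends similar comparisons to onset and offset and to further measures. Section 5.1 assumes that "a sample size of 25 qualified subjects (see study schematic) in each group is sufficient", without an effect size, SD or power.

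For significance, section 6 says: "A calculated P-value < 0.05 will be considered a significant difference between treatments". Sidedness is not stated. Although that sentence speaks of treatments, the only tests named are within-group, and the ANCOVA in section 6 is also run in each group. No between-group test is named.

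**The concern.** The choice of test depends on the data. Because the tests are within-group, the choice most naturally falls separately on each group, measure and visit. The text does not say so outright, but nothing in it prevents it.

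When changes are skewed, the two tests address different quantities. The t-test concerns the mean change. The signed-rank test concerns the centre about which signed ranks balance. If lag time is tested one way in the antiplatelet-naïve group and the other way on dual therapy, a difference in significance may partly reflect the test. The study aims to describe the effect across naïve, mono- and dual-therapy patients, and the within-group changes are the only comparisons with a stated test, so readers will set these p-values side by side.

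The undefined trigger also leaves room to settle the choice after the data are seen.

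**Working it through.** **Inputs from the documents.** Section 2.2 gives the "target enrollment number of 100 subjects (25 qualified subjects in each study group"), so 4 × 25 = 100. That is the only sample-size figure that can be checked. The per-test level is 0.05 (section 6). Section 8.5 says "Subjects who are prematurely withdrawn from the study will not be replaced" and no dropout rate is given, so the analysed number may fall below 25.

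**Assumptions.** Shapiro-Wilk at 0.05 (range 0.01 to 0.10 shown), two-sided tests, and the same change distribution in all four groups. The documents give no distribution for any measure, so a range of skew is shown.

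**Method.** 20,000 simulated samples of 25 per scenario. Each sample had a Shapiro-Wilk test, then an exact signed-rank test if that rejected, otherwise a one-sample t-test on the changes. Skewed changes were gamma (skew 0.5 to 1.4 and 2.0) or lognormal (skew 1.75), centred at mean zero. The Monte Carlo standard error of a 5% rate is √(0.05 × 0.95 / 20,000) = 0.15 points.

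**Mixing.** If q is the Shapiro-Wilk rejection rate in one group, the chance that four groups do not all get the same test is 1 − q⁴ − (1 − q)⁴. At skew 1.0, q = 0.372: 1 − 0.019 − 0.156 = 0.825. The maximum, at q = 0.5, is 1 − 2 × 0.5⁴ = 0.875.

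The last three columns give the rejection rate at a nominal 5% when the true mean change is zero.

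| Change distribution | q | Four groups not alike | Always t | Always Wilcoxon | Two-stage rule |
|---|---|---|---|---|---|
| Normal | 0.052 | 19.1% | 4.9% | 4.7% | 5.1% |
| Skew 0.5 | 0.126 | 41.6% | 5.1% | 5.2% | 5.5% |
| Skew 0.7 | 0.208 | 60.4% | 5.0% | 5.7% | 5.8% |
| Skew 1.0 | 0.372 | 82.5% | 5.4% | 6.9% | 7.1% |
| Skew 1.4 | 0.654 | 80.2% | 6.8% | 9.6% | 9.8% |
| Skew 1.75 | 0.629 | 82.5% | 6.7% | 10.3% | 10.2% |
| Skew 2.0 | 0.922 | 27.8% | 7.7% | 13.9% | 14.0% |

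**Sensitivity to the unstated level.** For Shapiro-Wilk levels 0.01 to 0.10, mixing under normality runs from 4% to 35%, and at skew 1.0 from 55% to 88%.

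**Paired values.** With correlated lognormal pre and post values (assumed correlation 0.7, 5,000 samples) and no drug effect, mixing was 44%, 75% and 84% at log-SD 0.3, 0.5 and 0.8. With a 20% reduction it was 50%, 79% and 81%. Mixing therefore does not depend on an artificial skewed null.

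**Error with paired values.** If the drug does nothing and pre and post values are exchangeable, the changes are symmetric however skewed the raw measure is. The two-stage error was then 4.9 to 5.5%. A separate run on lognormal and gamma pairs gave 4.4 to 5.6%.

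**The case against.** A reader might infer that the pre-test itself inflates the false-positive rate to 7 to 10%. The figures do not support that. The two-stage rate is almost the same as that of Wilcoxon fixed in advance (7.1% against 6.9% at skew 1.0; 10.2% against 10.3% at skew 1.75), and part of the excess is already in the plain t-test. The rest arises because Wilcoxon is scored against a mean null that it does not test. The inflation also needs changes that are skewed while their mean is zero, so a drug or time effect would have to reshape the distribution without moving its mean. That is possible, but nothing in the documents suggests it.

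A reader might also infer that the four groups' results cannot be compared at all. That goes too far. The choice affects the p-value only; changes can still be summarised in the same units in every group. Between-group comparison should not rest on lining up four p-values under any rule, and the absence of a named between-group test is a separate gap. When changes are symmetric, both tests have the same centre and mixing does little harm.

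The skew is assumed, and the figure of about 80% belongs to a band near the peak. The study is labelled exploratory. Multiplicity is also a larger source of error: 7 measures × 4 groups = 28 unadjusted primary within-group tests give 1 − 0.95²⁸ = 76% familywise error if independent.

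All of this limits the size of the point. What stands is that section 6 has no rule to keep one test per measure and no defined trigger.

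**Conclusion.** The point holds as one of consistency and pre-specification. Under the stated assumptions, a measure is not tested alike in all four groups about 19% of the time if changes are normal, 42% at skew 0.5 and about 80% at skew 1.0 to 1.75. At skew 2.0 the figure falls to 28%, because nearly every group then switches to Wilcoxon. Where changes are skewed, the within-group p-values for one measure can concern different quantities.

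The error rate is a secondary matter. It is about 7 to 10% for a zero mean change at skew 1 to 1.75, and about 5% when pre and post values are exchangeable.

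The conclusion rests on reading the choice as separate for each group, on the assumed Shapiro-Wilk level and distributions, and on 25 analysed per group. It is a minor point that is worth making because the remedy is cheap.

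**What to change.** Delete the Shapiro-Wilk step and the conditional switch from section 6. Before the data are examined, name one primary method per measure, used in all four groups and at all visits. For example, use the paired t-test with a 95% confidence interval on the change, or on the log-ratio for positive measures that the sponsor expects to be skewed. The documents do not show which measures those are, so the sponsor should list them. Report the Wilcoxon test in every group as a sensitivity analysis, described as a test of its own centre and not of the mean change. State that tests are two-sided.

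With one method fixed, mixing is 0%. For a zero mean change, the t-test on raw change has an error of 5.4 to 6.8% at skew 1.0 to 1.75, against 7.1 to 10.2% for the present rule.

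The cost is wording only, with no extra subjects, samples or visits. There are two downsides. A measure analysed as a log-ratio is reported as a percentage and not an absolute change, so section 5.2 should say so for that measure. The sensitivity analysis also adds a little work.

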Statistical Methodology: A very brief description of main elements of the statistical methodology to be used.

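### Between-group comparisons are part of the primary and secondary analyses, but Section 6 names no method for them, and its P < 0.05 sentence can attach a between-treatment label to a within-group test

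*Combined protocol and SAP*

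**What the plan says.** - **Section 5.2.1** defines the primary analysis as the change in three thrombelastography and four thrombin generation measures at maintenance, "compared to pre-dose within and between each treatment group". Section 5.2.2 uses the same within-and-between formula six more times for the secondary endpoints.
- **Section 5.1** calls the study exploratory ("This is an exploratory study; we assume that a sample size of 25 qualified subjects") and takes that number per group to be "sufficient to assess the difference in platelet inhibitory effect of vorapaxar 2.08 mg, administered alone or in addition to an antiplatelet agent".
- **Section 6** names the tests: "Within group analyses of change scores (pre and post vorapaxar) will be performed using a paired t-test", with the Wilcoxon signed ranks test if Shapiro-Wilk indicates non-normal change scores. Next comes the significance rule: "A calculated P-value < 0.05 will be considered a significant difference between treatments". The one further model is described thus: "A secondary ANCOVA analysis will be performed in each group to examine the factors" behind variation in change scores.
- **The synopsis** entry for statistical methodology is unfilled template text: "A very brief description of main elements of the statistical methodology to be used".

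**The concern.** A paired test asks whether the mean change in one cohort differs from zero. An ANCOVA run inside one cohort has no group term. Neither can estimate how much the change in one cohort differs from that in another, yet that comparison is part of the stated primary analysis and is the quantity used in Section 5.1 to justify the group size.

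Two things follow. First, the model, the covariates and the choice of which cohorts to contrast would be settled after the data are in. Second, the only significance sentence speaks of treatments being different while the tests before it compare a cohort with itself. A report could therefore follow Section 6 to the letter and present a within-group P-value as a between-treatment finding.

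**Working it through.** **1. Set the requirement beside the methods.**

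| Comparison asked for (5.2.1, 5.2.2) | Method named in Section 6 |
|---|---|
| Change within each group | Paired t-test or Wilcoxon signed ranks |
| Factors explaining change within a group | ANCOVA in each group |
| Change between groups | None |

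No two-sample test, ANOVA, pooled ANCOVA or mixed model appears elsewhere in the document. The synopsis, which could have filled the gap, holds a placeholder.

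**2. The plan's own figure.** Four groups of 25 give 4 × 25 = 100, as stated in Section 2.2. The 25 itself cannot be reproduced, because no effect size, SD, power or sidedness is given. Everything below is therefore in SDs of the change score, with assumed effects, n = 25 per group and two-sided alpha of 0.05.

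**3. What a within-group verdict says about a between-group difference.** The power p of the paired t-test comes from the noncentral t distribution with 24 df and noncentrality d√25. For two independent cohorts with the same true change d, the chance that one is significant and the other is not is 2p(1 − p).

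| d (SD) | p | 2p(1 − p) |
|---|---|---|
| 0 | 0.050 | 0.095 |
| 0.2 | 0.161 | 0.27 |
| 0.4 | 0.484 | 2 × 0.484 × 0.516 = 0.50 |
| 0.5 | 0.670 | 0.44 |
| 0.6 | 0.821 | 0.29 |
| 0.8 | 0.970 | 0.059 |

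The reverse error also occurs. With true changes of 1.2 and 0.8 SD, both paired tests are significant in 97% of trials, so a real difference of 0.4 SD leaves no trace in the verdicts.

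**4. What a proper between-group contrast can deliver.** In an unadjusted model over four groups there are 100 − 4 = 96 residual df. The 95% CI half-width for a difference between two groups is t(0.975, 96) × √(2/25) = 1.985 × 0.2828 = 0.56 SD. Power reaches 80% at a difference of 0.80 SD and is 29% at 0.4 SD.

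**5. Effect of adjusting for the V2 value.** Assume equal V2 and V4 variances and correlation r between them. The residual SD is then √((1 + r)/2) change-score SDs. With 95 df the half-width is 0.45, 0.49 and 0.55 SD at r = 0.3, 0.5 and 0.9.

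**The case against.** The study is labelled exploratory, and neither hypothesis in Section 1.1 is a contrast between cohorts: one concerns the effect of vorapaxar in patients on standard regimens, the other a larger effect in patients with high clot strength. Section 5.2.1 also fixes the measures, the time point and the baseline, so a difference in mean change is readily inferred as the quantity of interest. And since Section 6 defines its change scores as pre and post vorapaxar, the P < 0.05 sentence may mean just that, or be a general alpha.

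All of this stands, and it limits the point. It does not supply a model, covariates or a contrast set, and under either kinder reading of the sentence the between-group comparison still has no method.

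Three stronger readings are not supported:

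- A reader might infer that the plan intends to compare significance verdicts across cohorts. It nowhere says so. The disagreement rates show what would happen under that misuse, not what the plan will do.
- A reader might infer that the primary analysis has no test at all. Its within-group part has one.
- A reader might see an error in the per-group ANCOVA listing "antiplatelet response to EC ASA and clopidogrel, smoking, etc" among its variables, because Group 1 takes neither drug and Groups 2 and 3 take one each. The sensible reading is that each response enters only where the drug is taken.

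**Conclusion.** The point holds and should be fixed. The plan asks for between-group comparisons seven times and gives no method for any of them, and its one significance rule, taken literally, puts a between-treatment label on tests that look only within a cohort.

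How much harm follows depends on assumptions that the documents do not settle. If verdicts were compared, the disagreement rate for equal true changes would range from 6% (0.8 SD) to 50% (0.4 SD). If they never are, the cost is an unspecified analysis chosen after the data are seen. A specified contrast would not be powerful at this sample size: its gain is a defined estimate with an honest interval.

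**What to change.** In Section 6:

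1. **Between-group model.** Fit one linear model over all four groups to the V4-minus-V2 change, with group as a factor and the V2 value as covariate. Name this adjusted model as the single decisive analysis and show the unadjusted contrast as supportive only; otherwise the choice between the two stays open. Pre-state the contrasts, for example Groups 2, 3 and 4 each versus Group 1 (labelled the control group in Section 4.8) and Group 4 versus Group 3, or all six pairs. Report each difference in mean change with a 95% CI as exploratory, with no multiplicity-controlled claim of significance. If the sponsor wants significance verdicts, use one adjusted level with CIs to match. State the approximate precision: unadjusted half-width 0.56 SD, and 80% power for 0.80 SD at two-sided 0.05.
2. **Significance sentence.** Replace it with: *All tests are two-sided. A within-group P < 0.05 supports a pre- versus post-vorapaxar change in that group only; differences between groups are judged only from the pre-stated between-group contrasts, which are exploratory.*
3. **Interpretation.** State that the contrasts are non-randomized associations, and that Groups 1 and 2 (multiple risk factors) and Groups 3 and 4 (prior MI or PAD) are different populations.

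**Cost.** Wording and a little more analysis. Table 1 already schedules pharmacodynamic samples at V2 and V4 for all subjects. The adjusted model assumes a common V2 slope across groups, which can be checked. Adjusted and unadjusted contrasts can diverge when V2 values differ between cohorts. For an assumed gap of 0.5 V2-SDs with equal V2 and V4 variances, they differ by 0.5(1 − r)/√(2(1 − r)), which is 0.30, 0.25 and 0.11 change-score SDs at r = 0.3, 0.5 and 0.9. That is why both should be shown and one named in advance.
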